5.2 Patient Enrollment

(1) For patients who have been on drugs subject to the HRD cooperative investigation at the time of the contract or will start to receive them during the survey period, the investigator/subinvestigator should enter required information (medical record number or identification number, patient's initials [as necessary], gender, birth date [as necessary, age; e.g., age group], pregnancy status, inpatient/outpatient status, name of the drug surveyed and start date of treatment) on the enrollment screen of the EDC system, and send it using the user's ID and password issued for each investigator/subinvestigator. The patients' enrollment numbers will be issued by the EDC system. The sites that cannot connect to the external network should send or collect the data after inputting them in the SPC.

Patients who have been continuously on the drugs subject to the HRD cooperative investigation will be automatically continued to be enrolled based on data of the previous CRFs.

(2) The CRO should, as necessary, report the status of patient enrollment to the applicable companies using an HRD cooperative investigation control chart.

(3) Sites having a markedly high number of patients should first understand an expected number of new patients and then enroll new patients in the order of the re-enrollment of new patients on the day of enrollment in the HRD cooperative investigation among continuing patients and patient verification by the sites. The ratio of the number of re-enrolled continuing patients and newly enrolled patients should be adjusted. Overall, approximately 40 patients per investigator should be enrolled.

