5.7 Handling of Patients with ADRs

- (1) When ADRs, etc. (including those for which the causal relationship is unknown) suspected to be caused by the drug occurred, the investigator/subinvestigator should immediately notify them to the CRO or complete required information in the “HRD Cooperative investigation: Spontaneous Reporting Form for ADRs, etc.,” which has been provided beforehand, and fax it to the CRO.
- (2) When learning the onset of ADRs, etc. (including those for which the causal relationship is unknown) associated with Celsentri from healthcare professionals, an MR should immediately fill out the “HRD Cooperative investigation: Spontaneous Reporting Form for ADRs, etc.” and directly fax it to the CRO. When receiving a Spontaneous Reporting Form, it should be immediately faxed to the CRO.
- (3) When an anti-HIV infection drug, for which the causal relationship cannot be ruled out, was concomitantly used, an MR should obtain prior consent of the investigator for reporting ADR information to a company related to the concerned drug.
- (4) When identifying ADR information in data sent from the investigator, the CRO should notify it to the applicable company.
- (5) The applicable company should assess and analyze this ADR information and, as necessary, instruct a detailed investigation to the CRO. The CRO should request the investigator to input and send the latest information using the EDC system and inform it to the applicable company after receiving the said information.

6. Planned Period of the Survey

The survey will be started in April 2009. The patient enrollment period will be until the end of the 8th year.

Enrollment period: April 1, 2009 to March 31, 2017

7. Investigation Items

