7.10 Priority Investigation Items

In this survey, the occurrence of the following items will be defined as the priority investigation items:

(i) Effect on immune competence

[Reason for selection]

Nonclinical or clinical studies of Celsentri have not suggested that Celsentri treatment increases infections, malignancies, etc. However, there is a concern that Celsentri may affect immune competence (onset of infections, malignancies, etc.) based on its mechanism of action to inhibit CCR5 chemokine receptors.

[Investigation method]

By focusing on the onset of AEs such as infections and malignancies, they will be tabulated by the causal relationship with Celsentri and stratified according to patient background characteristics to evaluate the safety of Celsentri.

(ii) Effect on liver function

[Reason for selection]

No clinical data obtained so far shows the effect of Celsentri on liver function compared with placebo. However, a nonclinical study in rats revealed high exposure to the liver. CCI

Also, a Phase III study of Celsentri (A4001026) reported cases of liver disorder suspected to be related to maraviroc and resulted in liver transplantation.

[Investigation method]

By focusing on the onset of abnormal liver function test values and AEs mainly corresponding to hepatobiliary disorders according to the System Organ Class (SOC) of the MedDRA, they will be tabulated by the causal relationship with Celsentri and stratified according to patient background characteristics to evaluate the safety of Celsentri.

(iii) Effect on the cardiovascular system

[Reason for selection]

Clinical studies and a Phase IIb/III study to evaluate QT prolongation revealed no clinically significant effect on the QTc interval. In addition, the onset of myocardial infarction and ischemic heart disease during Celsentri treatment is rare, and their incidence is the same as that in this population with a history of treatment. However, nonclinical studies suggested that Celsentri might prolong the QT interval at concentrations above the therapeutic concentration.

[Investigation method]

By focusing on AEs mainly corresponding to cardiac disorders according to the SOC of the MedDRA, they will be tabulated by the causal relationship with Celsentri and stratified according to patient background characteristics to evaluate the safety of Celsentri.

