DRUG USE INVESTIGATION FOR HIV INFECTION PATIENTS OF MARAVIROC

- HRD Joint Survey -

STATISTICAL ANALYSIS PLAN

CELSENTRI Tablets 150 mg Statistical Analysis Plan

Outsourced by
Product name
Pregnant Women
Prepared by

ViiV Healthcare K.K.
CELSENTRI Tablets 150 mg Drug Use Survey, Special Drug Use Survey for
CMIC-PMS Co., Ltd. PPD

<General Definitions>

Re-examination period	
Number of report	Survey period
1st	2008/12/25 (H20) - 2009/2/5
2nd	2/6/2009 (H21) - 8/5/2009
3rd	8/6/2009 (H21) - 2/5/2010
4th	2/6/2010 (H22) - 8/5/2010
5th	8/6/2010 (H22) - 8/5/2011
6th	8/6/2011 (H23) - 8/5/2012
7th	8/6/2012 (H24) - 8/5/2013
8th	8/6/2013 (H25) - 8/5/2014
9th	8/6/2014 (H26) - 8/5/2015
10th	8/6/2015 (H27) - 8/5/2016
11th	8/6/2016 (H28) - 8/5/2017
12th	8/6/2017 (H29) - 8/5/2018
13th	8/6/2018 (H30) - 12/24/2018
Re-examination	12/25/2008 (H20) - 12/24/2018
Date conversion	
When you calculate dates for aggregation, make the following replacement: Replace the date “AA=early in the month” with 05, “BB=middle of the month” with 15, “CC=late in the month” with 25, and “DD=around” with 01. Replace “20EEEEEE=continued” with “the outcome confirmation date of the patient”. If nothing is provided, enter “entry date”. The new survey does not have entries of 20EEEEEE, but enter 20EEEEEE for continued administration if “entry date” is found. When you need to replace any inappropriate date (such as Day 00), add the following process: When the date in “first administration date” is not appropriate as a date, choose the final date of the month. When the month and date in “first administration date” are not appropriate as a date, enter “1231”. When the date in “final administration date” is not appropriate as a date, enter “01”. When the date in “onset date of adverse event” is not appropriate, enter “01”. When the date in “laboratory test date” is “00” or “99”, enter “01”. Only a date after the approval date (=December 25, 2008) should be used for CELSENTRI Tablets (when the first administration date comes before the approval date, replace it with the approval date).

Date unit	A week has 7 days, a month has 30 days, and 1 year has 365 days.
Prior to administration	It should be within 30 days prior to the first administration of CELSENTRI Tablets and be the closest date to the first administration date (the administration date is also included).
Displayed digit	Decimal numbers should be rounded to the second decimal place.

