Complications	Use the complications provided in the CRF at the first administration of CELSENTRI Tablets. The events that occurred and did not recover before the first administration of CELSENTRI Tablets in the 'adverse event' column. [Stratification] Absence, Presence, Unknown/not provided
Type of complications	Complications provided in the CRF at the first administration of CELSENTRI Tablets <Multiple-answers are acceptable in this column> In addition, reflect the ViiV Healthcare K.K.'s instruction for data amendment. [Stratification] • "Haemophilia": complications are present "1. Haemophilia"

	
•"Liver disorder": the disease selected as liver disorder in 'complication is present': 3. Hepatitis A", "4. Hepatitis B", "5. Hepatitis C", "6. Other liver disorders", or "8. Others"

The mean daily dose	
The mean dose for "administration period" Even if "administration period" is unknown, the provided value should be regarded as the mean when there is no change in "the dose". [Stratification] >minimum and < 2 tablets, 2 tablets, >2 tablets and <maximum, unknown/not provided

Dosing frequency	
Calculate the number of dosing in a day. [Stratification] 1, 2, ≥3 and ≤maximum, unknown/not provided

Administration period	
\sum (final administration date - first administration date+1). Exclude the washout period. [Stratification] ≤180 days, >180 and ≤365 日、 >365 and ≤730 日、 >730, unknown/not provided

Administration period <cumulative>	
Count "the number of patients" by accumulating "administration period", count "the number of patients with adverse reactions" based on the "administration period" until the first adverse reaction occurred, and count "the number of adverse reactions" based on the "administration period" until the applicable adverse reaction occurred. Exclude the washout period. [Stratification] ≤180 days, >180 and ≤365 日、 >365 and ≤730 日、 >730, unknown/not provided

Total dose	
\sum {(Final administration date - First administration date+1) × a daily dose}. Exclude the washout period.[Stratification]≤360 tablets, >360 tablets and ≤730 tablets, >730 tablets and ≤1460 tablets, >1460 tablets, unknown/not provided

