Total dose <cumulative>	
Count "the number of patients" by accumulating "total dose", count "the number of patients with adverse reactions" based on the "total dose" until the first adverse reaction occurred, and count "the number of adverse reactions" based on the "total dose" until the applicable adverse reaction occurred. Exclude the washout period. [Stratification] ≤360 tablets, >360 tablets and ≤730 tablets, >730 tablets and ≤1460 tablets, >1460 tablets, unknown/not provided

Continued/discontinued	
Display 'continued/suspended' of the final administration period throughout a year. [Stratification] Continued, Suspended, Unknown/not provided

Presence/absence of concomitant drugs	
If there is a drug concomitantly used in the "administration period" of CELSENTRI Tablets, select "2=present". If there is a drug concomitantly used at least for a day, select "2=present". Of note, if only one date is overlapped when two anti-HIV drugs are used on the same day (as the first administration for one and the final administration for the other), it should be regarded as "replacement" and not handled as a concomitant drug. [Stratification] Absence, Presence, Unknown/not provided

Number of concomitant drugs	
Number of types of concomitant drugs used in the "administration period" of CELSENTRI Tablets Drugs concomitantly used at least for a day. Of note, if only one date is overlapped when two anti-HIV drugs are used on the same day (as the first administration for one and the final administration for the other), it should be regarded as "replacement" and not counted as a concomitant drug. [Stratification] ≤2 drugs, ≥3 and ≤5 drugs, ≥6 drugs

Type of concomitant drugs	
Count the breakdowns of designated concomitant drugs. Of note, when a patient used multiple drugs in the same classification, count the drugs as one. <Multiple-answers are acceptable in this column> [Stratification] Anti-HIV drug, Other anti-virus drugs, Others

Number of concomitantly-used anti-HIV drugs	Number of types of anti-HIV drugs used in the “administration period” of CELSENTRI Tablets Drugs concomitantly used at least for a day. Of note, if only one date is overlapped when two anti-HIV drugs are used on the same day (as the first administration for one and the final administration for the other), it should be regarded as “replacement” and not counted as a concomitant drug. [Stratification] a single-use drug, 1 drug, 2 drugs, 3 drugs, ≥4 drugs

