Data on the incidence of adverse reactions per patient background	Display the incidence of adverse reactions per patient background for each patient.
A list of the onset status of adverse reactions/infections per patient background	Prepare a list of the onset status of adverse reactions/infections for each patient background item below. Follow ‘adverse reactions’ of <General Definitions> for the onset status of adverse reactions while follow the above <Handling of Items> for the definition of each patient-background item. © Displayed items: primary disease, sex, presence/absence of pregnancy, age, inpatient/outpatient classification, treatment history of HIV infection, race, route of transmission, duration of disease, medical history, allergy, complication, type of complication, renal disorder, liver disorder, the mean daily dose, administration period, administration period [cumulative], total dose, total dose [cumulative], continued/discontinued, concomitant drug, number of concomitant drugs, type of concomitant drugs, number of concomitant anti-HIV drugs, type of concomitant anti-HIV drugs, presence/absence of haemophilia, haemophilia AB, CDC classification of severity prior to administration, concomitant treatment, blood coagulation factor (all cases and the cases with haemophilia)
Number of days to administer until the day on which adverse reactions first occurred	Prepare a table by number of days ≤ 180 days, 180 days < ≤ 365 days, 365 days < ≤ 730 days, 730 days <
The incidence of adverse reactions per concomitant drug	Prepare a table of incidence of adverse reactions regarding concomitant drugs per drug code (the first 7 digits). Follow “Co-administration” of <General Definitions> for the definition of co-administration.
A table of patient numbers per concomitant drug	Prepare the patient registration numbers for each drug code (the first 7 digits) regarding concomitant drugs with and without patients with adverse reactions. Follow “Co-administration” of <General Definitions> for the definition of co-administration.
The incidence of adverse reactions per complication	Prepare a table of incidence of adverse reactions per PT regarding complications and other contents. The definition of complications is applied to the patients with “complications” of <Definitions of Items>.

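### The SAP's time-on-drug displays for adverse reactions stop at one open row above 730 days, so no planned table shows whether the reaction rate changes after year 2 of a survey of about 8 years.

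*SAP*

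**What the plan says.** **Time on drug.** In the SAP, Handling of items, the administration period and its cumulative version have the same rows: up to 180 days, 180 to 365 days, then ">365 and ≤730 日、 >730, unknown/not provided" (the character 日 means days). The cumulative version places reactions by exposure up to onset: "count 'the number of adverse reactions' based on the 'administration period' until the applicable adverse reaction occurred". Under tables for the safety analysis group, the display of days to first adverse reaction ends in the same way: "365 days < ≤ 730 days, 730 days <".

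**Total dose.** Total dose and its cumulative version end with ">730 tablets and ≤1460 tablets, >1460 tablets, unknown/not provided".

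**Length of observation.** Protocol section 6 gives "Enrollment period: April 1, 2009 to March 31, 2017". Under Protocol 5.2, continuing patients "will be automatically continued to be enrolled based on data of the previous CRFs", so one patient can contribute several years. Under Date conversion in the SAP's General Definitions, "when the first administration date comes before the approval date, replace it with the approval date". Counted exposure can therefore start on 25 December 2008.

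**Late safety.** Protocol 7.10(i) records a concern that "Celsentri may affect immune competence (onset of infections, malignancies, etc.) based on its mechanism of action".

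**The concern.** The cumulative item and the days-to-first-reaction table are the SAP's own means of relating reactions to time on drug. Both have three rows for the first two years and one for everything later. The cumulative dose item adds no late resolution at 2 tablets a day. Attachment Form 2 divides results by calendar survey period, not by time since a patient's first dose, so it does not fill the gap.

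A survey of this length is a natural source of information on reactions that appear after years of treatment. As planned, a reaction rate that rises after year 3 or year 5 produces the same kind of table as a rate that stays flat.

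**Working it through.** **Inputs.** From the SAP: day cut-offs 180, 365, 730; tablet cut-offs 360, 730, 1460; approval date 25 December 2008; a year of 365 days; data lock 26 March 2018. From the Protocol: enrolment 1 April 2009 to 31 March 2017; results entered each year up to the end of March. Neither document gives an accrual pattern, a stopping rate or the number of patients treated beyond 730 days.

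**1. Do the tablet rows match the day rows?** At 2 tablets a day, 2 × 180 = 360, 2 × 365 = 730 and 2 × 730 = 1460. All three match. At other intakes the last row opens elsewhere: 1460/1 = day 1460, 1460/4 = day 365 (arithmetic only).

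**2. How much of the possible time range is in the open row?** Share = (maximum days − 730) / maximum days, counting both end dates.

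| Exposure counted | Maximum days | Days in open row | Share |
|---|---|---|---|
| 1 Apr 2009 to 31 Mar 2017 | 2,922 | 2,192 | 75.0% |
| 25 Dec 2008 to 31 Mar 2017 | 3,019 | 2,289 | 75.8% |
| 25 Dec 2008 to data lock | 3,379 | 2,649 | 78.4% |

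These are shares of the longest possible exposure, not of patients or events.

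**3. How much exposure is in the open row?** Assume starts spread evenly over T = 3,019 days, follow-up to 31 March 2017, and a constant yearly stopping proportion s, with λ = −ln(1 − s)/365. The proportion of all patients still on drug and under follow-up at day t is (T − t)/T × exp(−λt). The share of patient-days beyond day a is the integral of (T − t)·exp(−λt) from a to T, divided by the same integral from 0 to T.

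- With s = 0 the share beyond 730 reduces to (2289/3019)² = 0.758² = 57%.
- Patients reaching day 730: 0.758 × (1 − s)². With s = 30%: 0.758 × 0.49 = 37%.
- Patients reaching day 1825: (1194/3019) × (1 − s)⁵. With s = 30%: 0.395 × 0.168 = 7%.

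| Yearly stopping | Patient-days beyond 730 | Patients reaching 730 | Patients reaching 1825 | Patient-days beyond 1825 |
|---|---|---|---|---|
| 0% | 57% | 76% | 40% | 16% |
| 10% | 50% | 61% | 23% | 11% |
| 20% | 41% | 49% | 13% | 7% |
| 30% | 33% | 37% | 7% | 4% |
| 50% | 18% | 19% | 1% | 1% |

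**4. What can the single row hide?** Take 20% stopping: 41.2% of patient-days lie beyond 730 and 6.9% beyond 1825, so 34.3% lie between. Suppose the rate doubles at day 1825. The row total equals that of a flat rate r if the rate before day 1825 is r × 41.2/(34.3 + 2 × 6.9) = 0.857r. A doubling after year 5 and a flat rate then give the same expected count in the row.

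**The case against.** **The data are not lost.** A reader might infer that the late pattern cannot be recovered. The documents do not support that. The event lists give days to onset. The SAP also plans a patient line list for everyone with a collected form, and per-patient data on reactions by background. The related background table includes administration period and total dose. The mock-ups are not shown, so the exact columns cannot be confirmed, but re-tabulation may well be possible. What stands is that no planned table does it.

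**Malignancy.** A reader might infer that the open row hides late malignancies. These tables count all adverse reactions by company assessment. Protocol 7.10(i) asks for infections and malignancies as adverse events, by causal relationship and background. Malignancies judged unrelated never enter these rows, and related ones are mixed with every other reaction. Finer rows would not answer that item.

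**Not every late reaction falls in the open row of every display.** The days-to-first-reaction table places a patient by the first reaction, so a late reaction after an early one is not shown there as late. The non-cumulative items place patients by total exposure, so their open row also contains early reactions of long-treated patients. The concern therefore rests on the cumulative and days-to-first-reaction displays.

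**Part of the remedy seems to exist.** The cumulative item counts patients by accumulated administration period, which appears to give the number reaching each row. That count alone does not suffice: rows of unequal width also need patient-days.

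**The size depends on assumptions.** This is fair. Protocol 5.2 also lets large sites adjust the ratio of continuing to new patients, which could shorten follow-up; the calculation ignores this.

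**Tables may change.** The SAP's closing note allows table forms to change with the results. That permits finer rows but does not plan them.

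**Conclusion.** The concern holds as a tabulation weakness in the cumulative administration-period, cumulative total-dose and days-to-first-reaction displays. It is neither a contradiction nor an error in the plan, since the Protocol prescribes no duration rows.

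The fixed facts are the open row above 730 days and a possible exposure of up to 3,019 days if counting ends on 31 March 2017. The 33 to 57% of patient-days rests on even starts and 0 to 30% yearly stopping. At 50% stopping it is about 18%, and the case for finer rows weakens accordingly. Recoverability depends on mock-ups not available here. A cheap improvement is justified; a claim that late reactions are lost, or that late malignancy is concealed by this choice, is not.

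**What to change.** In the cumulative administration-period and days-to-first-reaction displays, replace the last row with >730 to ≤1095, >1095 to ≤1825 and >1825 days. Split cumulative total dose at the matching points, 2 × 1095 = 2190 and 2 × 1825 = 3650 tablets.

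For each row, give the number of patients entering it and the patient-days at risk, excluding washout. For first reactions, count a patient's days only up to the first reaction. Read the rows descriptively. Splitting the non-cumulative items is optional, because they do not place reactions by onset time.

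The cost is two more rows per display and a patient-days column: programming only, with no new data. The downside is sparse last rows; under the assumptions above, 7% of patients reach day 1825 at 30% yearly stopping and 1% at 50%.
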